8 EFFICACY EVALUATION

8.1 EFFICACY ENDPOINT(S)

8.1.1 Primary Efficacy Endpoint

The primary efficacy analysis will be included in a separate analysis plan and is not covered in this SAP.

8.1.2 Secondary Efficacy Endpoint(s)

The secondary efficacy analysis will be included in a separate analysis plan and is not covered in this SAP

8.1.3 Exploratory Efficacy Endpoint(s)

- Mean total lasering time (sec). Lasering time is captured in minutes and seconds but will be converted entirely to seconds for analysis.
- Difference in means of total lasering time between groups
- Number of subjects receiving subsequent additional interventional stone procedures (URS-LL, SWL)) for stone(s) that were treated in the AEROLITH study
- Number and percentage of subjects receiving subsequent additional interventional stone procedures for stone(s)
- Number of secondary stone treatments
- Number of subjects taking prescription pain medication for managing stoneassociated pain prior to treatment, post treatment, at Day 14 and at Day 30(defined as a medication categorized as a Pain Medication and answered "Yes" to "Medication taken for Kidney Stones?")

8.2 EFFICACY ANALYSIS

8.2.1 Primary Efficacy Analysis

The primary efficacy analysis will be included in a separate analysis plan and is not covered in this SAP.

8.2.2 Supportive and Sensitivity Analyses of the Primary Endpoint

The primary efficacy analysis will be included in a separate analysis plan and is not covered in this SAP.

8.2.3 Secondary Efficacy Analyses

The secondary efficacy analysis will be included in a separate analysis plan and is not covered in this SAP.

8.2.4 Exploratory Efficacy Analyses

Mean Total Lasering Time

Mean total lasering time (sec) will be summarized descriptively overall and by treatment group and analyzed as a numeric endpoint using the ITT population. A two-sided t-test with equal variances assumed will be used to evaluate the null hypothesis that mean time is similar in both groups. A 95% two-sided CI for the mean difference will be provided.

An ANOVA will be used to evaluate mean total laser time as a function of location, treatment, and location-treatment interaction. Least square means for the treatment effects and difference of least square means will be provided with the associated p-values.

Pseudo SAS Code:

```
ods output diff=diff;
ods output LSMeanDiffCL=pdiff;
ods output LSMeans=lsm;
```

```
proc glm data = <DATA> plots=none;
    class <TREATMENT> <LOC>;
    model <TIME> = <TREATMENT> <LOC> <TREATMENT>*<LOC>;
    lsmeans <TREATMENT>/alpha=0.05 cl pdiff;
run;
```

Additional Interventional Stone Procedures for Treated Stone(s)

The number and percentage of subjects receiving subsequent additional interventional stone procedures for stone(s) that were treated in this study will be summarized overall and by treatment group using the ITT population. A Likelihood-Ratio chi-square test will be used to evaluate the null hypothesis that the proportion of subjects with at least one secondary stone treatment is equal in both groups. The two-sided 0.05 p-value will be reported.

```
Pseudo SAS Code:
ods output ChiSq=chisq;
proc freq data = <DATA>;
tables <TREATMENT>*<STREAT>/chisq;
run;
```

Where,

<DATA> is the dataset containing at the minimum, treatment and a binary variable for whether a subject has received additional interventional treatment for stone(s) <TREATMENT> is the randomized treatment

STREAT> is the binary variable for whether a subject has received additional interventional treatment for stone(s)

Prescription Pain Medication for Kidney Stone-Associated Pain

The number and percentage of subjects who take prescription pain medication for managing stone-associated pain will be summarized by timing (prior to treatment or post-treatment), drug class, and preferred term, overall and by treatment group for the ITT and PP populations.

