5.7. Inclusion Criteria

- 5.7.1. Male or female aged \geq 18 years to \leq 75 years
- 5.7.2. Provides written informed consent
- 5.7.3. Patients with at least one urinary stone measuring 6mm or greater (but no more than a cumulative diameter of 20mm) located proximally to the iliac vessels on one side may be treated.

Note 1: Punctate stones measuring $\leq 2mm$ do not count in the cumulative diameter limit. **Note 2:** Some corroborating imaging may be required to exclude a patient if the investigator suspects that the stone has moved to middle/distal ureter (e.g. change in symptoms, an increase in serum creatinine).

5.7.4. Urinary stone(s) should be apparent on a CT scan within 60 days prior to study enrollment.
 Stone assessment will be conducted using CT imaging following CLIN-0025:
 AEROLITH IDE Study Screening Guide

Note 1: Soft tissue window will be used for stone measurement. Window width/level adjustments will be applied as necessary by the reviewer to improve stone evaluation. A bone window may help distinguish stones from ureteral stents. The region of interest will be magnified (approximately 400%) by the reviewer to clearly visualize the stone outline. For details, please refer to CLIN-0003. **Note 2:** If CT imaging has not been conducted yet for the patient, please follow CT image acquisition parameters detailed in CLIN-0002: Image Acquisition Protocol, AEROLITH Study

- 5.7.5. Patients with bilateral stones are allowed but only one side may be treated. Only the treated side will be evaluated for safety and effectiveness.
- 5.7.6. Patient may enter the study with a stent in place.

5.7.7. Patients presenting with absence of a Urinary Tract Infection as confirmed using urinalysis

Note: If the urinalysis is more than 7 days removed on the day of the procedure, a urinalysis and confirmation that the patient is free of UTI symptoms should be performed on the day of the procedure for the patient to be eligible to participate in the study.

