10. STATISTICAL METHODS

10.1. General Considerations

The study results will be reported using descriptive summaries and data will be made available in listings or electronic format as required. The data will be summarized according to randomized treatment group (investigational arm and control arm). Inferential analyses will be performed for the primary endpoints and other endpoints as outlined below. For continuous variables, descriptive statistics will include means, standard deviations, medians and ranges. Categorical variables will be summarized in frequency distributions and reported with the count and percentages. Percentages will be calculated based on observed values. Except for the primary effectiveness endpoint analyses, a two-sided p-value less than or equal 0.05 will be considered statistically significant. The primary effectiveness analyses p-values associated with statistical significance are outlined below. Where reported, all confidence intervals will be two-sided 95% CIs.

A separate Statistical Analysis Plan will be constructed with additional detail on statistical considerations and content of tables, listing and figures from the various data analyses. Statistical analyses will be performed using SAS (version 9.4 or higher, SAS Institute Inc. Cary, NC), R (version 3.0 or higher, R Foundation for Statistical Computing, Vienna, Austria) or other widely accepted statistical or graphical software.

Results will additionally be stratified according to stone location (the upper (superior) pole, lower (inferior) pole, and interpolar region of the kidney, pelvis of the kidney, and proximal ureter) and stone diameter (< median, > median where the median is based on all ITT subjects).

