In addition, the Farrington-Manning test will be used to complete the analysis using the observed data. The two-sided 95% CI for the difference in observed data rates will be provided as well as the p-value. Note that all Farrington-Manning tests variances will be based on the sample variance under the null assumption the null groups results are equal. A tipping point analysis will be provided for evaluating the impact of missing data by imputing at the possible distribution of unavailable responses in the ITT populations. The treatment success analysis will also be completed in the per- protocol population.

The homogeneity of the treatment response will be evaluated using the available data and a logistic model of treatment success as a function of treatment, study site, and a site-treatment interaction. A p-value of less than or equal to 0.15 in the site-treatment term will be considered evidence of heterogeneity of the treatment effect across sites. In addition, as an exploratory analysis, a logistic model will be used to if stone location is associated with response or a location-treatment interaction.

10.7. Secondary Endpoint Analysis

The secondary endpoint is defined as:

Total radiant energy (TRE): Mean value of laser energy, measured in kilojoules, with laser energy values recorded and displayed by the pulsed laser unit used in the procedure, with the laser energy value for each procedure normalized by the stone cross-sectional area. For this purpose, the stone cross-sectional area is calculated by taking the product of the two largest stone size measurements on the preprocedure CT; for subjects with more than one stone treated in the index procedure, the stone cross-sectional area is calculated as the sum of the stone cross-sectional areas calculated individually for each treated stone. The mean value of laser energy for each arm is calculated by considering the normalized measured values for all study subjects in that arm.

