Normalized TRE will be summarized as a numeric variable. In addition, as the primary analysis is based on ratio of the means, the geometric mean and 95% CIs based on the back-transformation of the log values will be provided. The log-transformed values will also be summarized descriptively. All analyses of TRE will be based on available data. TRE is to be collected as part of the procedure and it few if any missing values are expected. If more than 4 subjects have missing TRE values, a MI analysis will be completed as a sensitivity analysis.

In support of the secondary hypotheses (Section 10.5), a t-test will be used to assess the difference in between groups in the means of the log-transformed normalized TRE value. If the two-sided 95% CI upper bound of the difference in the means is less than 0.223 (log 1.25) then secondary hypothesis 1 will be considered met and if bound is less than -0.0, the secondary hypothesis 2 will also be considered met. The one-sided p-values associated with the hypothesis will also be provided.

The ratio cut-off of 1.25 for the non-inferiority assessment was obtained based of review of papers describing total energy (Molina et al (2014), Humphreys et al (2018), and Rana, et al (2020)). Further, discussion with investigators indicated the endpoint could have considerable variability based on uniqueness of the individual subject, stone size, stone composition, and stone location. The Molina (2014) paper included analyses of total energy and found several significant predictors but at best the explained about half the variance (R2 = 0.524 for a multivariate model). Molina (2014) presented an exploration of total energy normalized by stone volume.

CONFIDENTIAL Page 35 of 53

Acoustic Enhancer Research on Laser Lithotripsy (AEROLITH) Clinical Study

Based on normalized TRE from the paper it appears as the ratio of the upper quartile to the median was approximately 1.6. The ratio of 1.25 would reflect a ratio of AE to control that would be close the control mean and well within variability associated with a single standard deviation. Hence, given the inherent variability of the measure, the use of 1.25 as a ratio to indicate non-inferiority normalized TRE is justified.

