5.1 ADJUSTMENTS FOR COVARIATES

5.2 NO ADJUSTMENTS FOR COVARIATES ARE PLANNED.HANDLING OF MISSING DATA

No imputation or adjustment for missing assessment data will be used.

See the following table for imputation rules for partial to fully missing or medication dates.

Missing Start Date Portion	Prior to Treatment	Same as Treatment Start Date	After Treatment Start Date
Day	Month and Year < Month and Year of first treatment:	Month and Year = Month and Year of first treatment:	Month and Year > Month and Year of First Treatment:
	Start Day = 1	Start Day = Day of	Start Day = 1
	Stop Day = last day of the month	first treatment Stop Day= last day of the month	Stop Day= last day of the month
Day and Month Define Day as above, then:	Year < Year of first treatment:	Year = Year of first treatment:	Year > Year of first treatment:
	Start Month = Jan	Start Month =	Month = Jan
	Stop Month = Dec	Month of first treatment	Stop Month = Dec
		Stop Month = Dec	
Day, Month, and Year	To be conservative, con date of first treatment, c date of last contact.	npletely missing start ompletely missing en	dates will be set to the dates will be set to the

Table 2:	Table of Imputation	Rules for Missing	Medication Dates

After following these imputation rules, if the start date is imputed as a date after the end date, the start date will be set to the end date to provide a positive duration for the event incidence.

Applaud's medical monitor will assess missing AE study medication relationship or severity which will be used analysis purposes.

No other imputation is planned for safety data.

5.3 **ASSESSMENT TIME WINDOWING**

No visit windows will be utilized in this study and all safety and efficacy assessment summaries will be based on the nominal protocol-specified assessment times. Thus, if the protocol specified Day 30 visit occurs on study Day 31, it will still be summarized as a "D30" assessment.

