6.4.2 Baseline Disease Status/Disease History

Disease history information will be collected on the Urinary Stone History form, which include:

- History of treatment procedures in study/treatment side (Yes/No)
- Existence of stent in place and whether the stent appears calcified or encrusted is in place
- Existence of radiolucent stones on KUB or Scout CT Imaging and the imaging modality used to access radiolucent stones if radiolucent stones are present

Disease status information will be collected on the Vital Signs/Physical Exam form and the Stone Location and Measurement form, which includes:

- Conduct of focused urogenital calculus physical exam and abnormality if conducted (Abnormal findings/No abnormal findings)
- Location of each stone (investigator reported)
- Largest diameter (mm) of each stone (investigator reported)
- Cumulative diameter (mm) of all stones (investigator reported)

Urinary stone history and stone location and measurement will be presented in separate bysubject listings and summarized together overall and by treatment group using the ITT, PP and Safety populations.

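### Total lasering time is compared without adjusting for stone size, although stone size is measured at baseline; the test is valid but gives away precision

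*SAP*

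**What the plan says.** SAP 8.2.4 (Mean Total Lasering Time), following Protocol 10.8, plans two analyses in seconds on the ITT population.

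- **t-test.** "A two-sided t-test with equal variances assumed will be used to evaluate the null hypothesis that mean time is similar in both groups", with a 95% CI for the mean difference.
- **ANOVA.** Location, treatment and their interaction, with least-squares means for treatment. The code asks for the default means, with no weighting option.

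Neither analysis has a stone-size term, and SAP 5.1 states "NO ADJUSTMENTS FOR COVARIATES ARE PLANNED". Protocol 10.1 sets the significance level: "Except for the primary effectiveness endpoint analyses, a two-sided p-value less than or equal 0.05 will be considered statistically significant".

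Stone size is available. SAP 6.4.2 lists the largest diameter of each stone and "Cumulative diameter (mm) of all stones (investigator reported". Protocol 6.3 and 10.7 compute a cross-sectional area from the pre-procedure CT. The eligible range is wide: "Patients with at least one urinary stone measuring 6mm or greater (but no more than a cumulative diameter of 20mm" (Protocol 5.7.3).

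TRE, recorded in the same procedure, is handled differently, "with the laser energy value for each procedure normalized by the stone cross-sectional area" (Protocol 10.7). It is also tested on the log scale, with a Wilcoxon test as confirmation.

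**The concern.** Lasering time can be expected to rise with stone burden. Leaving stone size out puts that variation into the error term and widens the confidence interval. Randomization is blocked by site, and no stone-size stratum is named (Protocol 7.3, SAP 2), so the design does not balance size either.

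Protocol 6.4.1 says that lower lasering time could be clinically important, and Protocol 9.2 links shorter lasering to less heat and less time under anesthesia. An inefficient comparison could leave that potential benefit unresolved when data already in hand would have sharpened it.

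The location model adds a smaller problem. With the interaction fitted, default least-squares means give each location the same weight however few subjects it holds.

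**Working it through.** **The plan's own figure.** Power is stated only for the primary endpoint. With 88 per arm, 55% vs 75% and one-sided 0.025, I obtain 79.96%, which agrees with the stated 80%. Inflating 88 per arm for 10% non-evaluable gives 98 per arm, or 196 in total. No power is stated for lasering time.

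**Inputs for lasering time**

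- Two-sided 0.05 (Protocol 10.1) and 98 per arm, since the time is recorded at the procedure.
- Assumed: lognormal time and a 20% true reduction.
- Assumed: total log SD of 0.5 to 0.7. The upper value is borrowed from Protocol 10.7, where the upper quartile of normalized TRE is about 1.6 times the median: ln(1.6)/0.6745 = 0.697.
- Assumed: stone size explains a share R² of log variance between 0.10 and 0.524. The top value comes from a cited model of total energy with several predictors ("at best the explained about half the variance (R2 = 0.524 for a multivariate model"), so for size alone it is an upper limit.

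**Planned raw t-test, closed form** (control mean set to 1)

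- Log SD 0.697: squared coefficient of variation = exp(0.697²) − 1 = 0.625. Pooled SD = √(0.625 × (1 + 0.8²)/2) = 0.716. SE = 0.716 × √(2/98) = 0.102. Then 0.20/0.102 = 1.955, and power is about Φ(1.955 − 1.96) = 50%.
- Log SD 0.5: squared coefficient of variation 0.284, pooled SD 0.483, SE 0.0689, ratio 2.90, power about 83%.

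**Log-scale ANCOVA, closed form.** SE = log SD × √(1 − R²) × √(2/98), and the effect is −ln(0.8) = 0.223. With log SD 0.697 and R² = 0.10, SE = 0.0945, the ratio is 2.36, and power is about 66%.

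**Simulation** (power, 20% reduction, 98 per arm, 10,000 trials per scenario; repeated runs agree within about 2 points)

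| Total log SD | R² | Raw t-test | Raw ANCOVA | Log ANCOVA |
|---|---|---|---|---|
| 0.5 | 0.10 | 84% | 87% | 91% |
| 0.5 | 0.30 | 83% | 93% | 96% |
| 0.5 | 0.524 | 84% | 98% | 99% |
| 0.70 | 0.10 | 51% | 55% | 64–66% |
| 0.70 | 0.30 | 52% | 62% | 75% |
| 0.70 | 0.524 | 51% | 78% | 90% |

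The simulated covariate has the correct functional form. A cruder size measure would recover less.

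**Alternative reading of 0.70.** The 1.6 ratio comes from energy already normalized by stone volume, so 0.70 may be the spread left after size. The total log SD is then 0.697/√(1 − R²), or 0.735 to 1.01. Raw t-test power falls to about 23% to 47%, and log ANCOVA gives about 60%.

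**Validity.** With no true effect, the planned t-test rejects in 4.3% to 5.3% of simulated trials.

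**Location model.** Relative to a main-effects estimate, equal weighting of K locations multiplies the variance by Σ(1/p_k)/K². Protocol 10.1 names five locations, so K² = 25. SAP 8.2.4 does not fix the number.

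- Rarest 10%, the others 22.5% each: (10 + 17.78)/25 = 1.111, so the SE rises 5%.
- Rarest 5%, the others 23.75% each: (20 + 16.84)/25 = 1.474, so the SE rises 21%.
- Uneven splits cost more: 40/20/15/15/10 gives 11%, and 40/30/15/10/5 gives 30%.
- An empty treatment-by-location cell makes the treatment mean non-estimable.

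**The case against.** - **Estimand.** Protocol 6.4.1 speaks of mean lasering time, and heat and anesthesia time are absolute quantities. A difference in seconds is a legitimate target, and a time ratio answers another question. This stands, and it is why the main change proposed is a covariate on the raw scale.
- **Inconsistency with TRE.** A reader might infer that the plan logs TRE because of skew and so contradicts itself here. The documents do not say so. Protocol 10.7 ties the back-transformed geometric mean to a comparison of ratios with a 1.25 margin, and its remarks on variability defend that margin. Lasering time has no ratio margin.
- **Size of the loss.** A reader might take 50% power as established. It rests on one borrowed spread and one assumed effect. With log SD 0.5 and a 25% reduction, the raw t-test already has about 96%, and little remains to gain.
- **Chance imbalance.** A reader might infer that imbalance in stone size biases the result. The t-test's standard error already allows for it, so the cost is precision.
- **Already covered.** Protocol 10.1 promises results split at the median stone diameter. SAP 5.6 plans no subgroup analysis, and SAP 13 does not list that omission as a change. The SAP therefore has no lasering-time comparison that takes size into account.
- **Low stakes.** The endpoint is exploratory, outside the tested sequence and not needed for study success (Protocol 6.6). This stands and limits the weight of the point.

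**Conclusion.** The concern holds as a matter of precision. An available baseline predictor is left out of both lasering-time models, and adding it raised power in every scenario examined with a true reduction. At 98 per arm and a 20% reduction, adjustment in seconds gains about 3 to 27 points (for example 84% to 87%, or 51% to 78%). A log-scale adjusted analysis gains about 7 to 39 points (84% to 91%, or 51% to 90%). The direction is secure if stone size predicts lasering time. The amount depends on a spread, an effect and a size correlation that the documents do not give for this endpoint, and the top of each range uses an upper-limit R². The planned p-value and confidence interval are valid, and neither study success nor the controlled type I error is touched. This is a worthwhile but minor improvement.

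**What to change.** In SAP 8.2.4, and with a matching exception in SAP 5.1:

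1. Make the main treatment comparison of lasering time an ANCOVA in seconds with baseline stone cross-sectional area (or cumulative diameter) as covariate. Report the adjusted difference with its 95% CI. Name the covariate, its form and its source (investigator or core laboratory) in advance.
2. Add an ANCOVA of log time, reported as a time ratio with 95% CI, as a supportive analysis.
3. Keep the unadjusted means as descriptive.
4. In the location model, take the overall treatment effect from main effects, or weight the least-squares means to the observed location frequencies. Test the interaction separately.

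The cost is SAP wording and a few lines of code. The data are already collected, and the SAP need only be signed before final database lock (SAP 1). The supportive ratio must be labelled clearly, because it does not estimate a difference in seconds.

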10.8. Additional Observations

Mean total lasering time will be analyzed as a numeric endpoint using the ITT Population. A two- sided t-test with equal variance assumed will be used to evaluate the null hypothesis that mean time is similar in both groups. A 95% two-sided CI for the mean difference will be provided. An ANOVA will be used to evaluate mean total laser time as a function of location, treatment, and location x treatment interaction. Least square means will be provided with ANOVA p-values.

The number and percentage of subjects receiving subsequent additional interventional stone procedures for stone(s) that were treated in the AEROLITH study will be summarized. A Likelihood-Ratio chi-square test will be used to evaluate the null hypothesis that the proportion of subjects with at least one secondary stone treatment is equal in both groups. In addition, the total number of secondary stone treatments will be summarized and a Cochran- Armitage trend test will be used to evaluate the null hypothesis that there is no trend in the number of stones between the groups.

Use and quantity of prescription pain medication for managing stone-associated pain will be characterized by timing and type of medication and will be summarized descriptively for the ITT and PP Population.

Residual stone size will be summarized descriptively as a continuous variable and rate of absence of residual stones as a categorical variable. These will be summarized for the ITT and PP Populations.

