3 DETERMINATION OF SAMPLE SIZE

A sample size of 196 enrolled and randomized subjects randomized 1:1 to the investigational arm (Acoustic Enhancer with URS-LL) and the control arm (URS-LL) was selected based on consideration of the primary endpoint. Assuming no more than 10% non-evaluable subjects, this provides a randomized sample size 176 subjects (88 per arm).

The primary hypothesis test for the treatment success outcome is as follows:

 $H_0: p_{AE} \le p_{Control} \text{ vs } H_1: p_{AE} > p_{Control}$

Where p_{AE} is the acoustic enhanced response rate and $p_{Control}$ is the control response rate (no acoustic enhancement). Using a one-sided 0.025 Farrington-Manning test, a 55% response rate in the control arm, and a 75% response rate in the investigational arm, the sample size provides 80% power for the analysis. The 55% control arm response rate is based on reported results for laser lithotripsy with CT-based follow-up as described in the protocol, while the 75% response rate in the investigational arm is based on exploratory clinical studies.

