4.1 LASERING TIME AND INTERVENTIONAL STONE PROCEDURES

While the secondary endpoint, total radiant energy (TRE), is a more rigorous and broadly applicable indicator of improved stone erosion, pitting and fragmentation through the generation of additional stone-fragmenting shockwaves, a demonstration of lower mean lasering time in the Acoustic Enhancer arm compared to the standard laser arm could be clinically important. Total lasering time (seconds) will be summarized as a numeric variable during the Treatment/Procedure [Day 1].

Interventional stone procedure(s) on stone(s) that were treated as part of the AEROLITH study will be identified as basketing for retrieval of stone material and other as collected on the procedure CRF page. This will be summarized categorically.

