13 CHANGES TO THE ANALYSES PLANNED IN THE PROTOCOL

In the protocol it is stated that the total number of secondary stone treatments will be summarized and a Cochran-Armitage trend test will be used to evaluate the null hypothesis that there is no trend in the number of stones between the groups. This was removed from the SAP. Because subjects exit the study 30 days after receiving treatment, this data is unlikely to be available.

No further changes exist between the protocol-defined statistical analyses and those presented in this statistical plan.

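### Re-intervention is compared by a likelihood-ratio chi-square with no sparse-data rule; its nominal 5% level would be about 9.5% if the common rate were near 2% per arm

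*SAP*

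**What the plan says.** For additional procedures on treated stones, SAP 8.2.4 states: "A Likelihood-Ratio chi-square test will be used to evaluate the null hypothesis that the proportion of subjects with at least one secondary stone treatment" is the same in the two groups. It adds: "The two-sided 0.05 p-value will be reported". The analysis set is ITT: counts and percentages for "stone(s) that were treated in this study will be summarized overall and by treatment group using the ITT population". Protocol 10.8 has the same test: "A Likelihood-Ratio chi-square test will be used to evaluate the null hypothesis". Protocol 10.1 treats any two-sided p-value of 0.05 or less, outside the primary effectiveness analyses, as statistically significant. Neither document gives an exact test or a small-count fallback.

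SAP 13 removes the Cochran-Armitage test on the number of secondary treatments and gives this reason: "Because subjects exit the study 30 days after receiving treatment, this data is unlikely to be available". The yes/no comparison built on the same events stays in.

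The source of the events is described in two ways. SAP 8.1.3 defines them as subsequent procedures and names URS-LL and SWL. SAP 4.1 says interventional procedures on treated stones "will be identified as basketing for retrieval of stone material and other as collected on the procedure CRF page". Under Protocol 8.2, basketing at the index procedure is a major protocol deviation.

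**The concern.** The likelihood-ratio statistic refers to the chi-square distribution only in large samples. With a handful of events in two equal arms it can reject too often. Re-intervention within about 30 days may well be uncommon, and the SAP itself doubts that related data will be available. Re-intervention is also an outcome that clinical readers find persuasive, so a p-value just under 0.05 that depends on the choice of test could be given more weight than it deserves.

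The source wording raises a different problem. If the yes/no variable (STREAT in the SAS code) were programmed from SAP 4.1, it could count deviations on the day of treatment in place of later re-treatment.

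**Working it through.** **Inputs.** SAP 3: "A sample size of 196 enrolled and randomized subjects randomized 1:1 to the investigational arm", so 98 per arm, and 88 per arm after 10% non-evaluable. SAP 8.2.4: likelihood-ratio chi-square, two-sided 0.05. The common event rate p is not in the documents and is varied here as an assumption.

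**Arm sizes reproduced.** For the primary endpoint (55% vs 75%, one-sided 0.025, n = 88), power = Φ{[0.20·√88 − 1.96·√(2·0.65·0.35)] / √(0.55·0.45 + 0.75·0.25)} = Φ{(1.876 − 1.322)/0.6595} = Φ(0.840) = 79.96%, against 80% stated. And 176/0.9 = 195.6, which rounds up to 196.

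**One table, 3 vs 0 events, 98 per arm.** Expected events are 1.5 per arm and expected non-events 96.5.
- Likelihood ratio: G² = 2[3·ln(3/1.5) + 95·ln(95/96.5) + 98·ln(98/96.5)] = 2(2.079 − 1.488 + 1.512) = 4.21, p = 0.040.
- Pearson: X² = 2·(1.5²/1.5) + 2·(1.5²/96.5) = 3.05, p = 0.081.
- Fisher: p = 2·(98·97·96)/(196·195·194) = 0.246.

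**Exact level.** All pairs of counts were enumerated from two independent Binomial(n, p) distributions with the same p. A test rejects when G² or X² is at least 3.841, or when Fisher p ≤ 0.05. Results at 98 per arm:

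| Assumed rate | Expected events, both arms | Likelihood ratio | Pearson | Fisher |
|---|---|---|---|---|
| 0.5% | 1.0 | 1.64% | 0.19% | 0.00% |
| 1% | 2.0 | 5.69% | 1.29% | 0.04% |
| 1.5% | 2.9 | 8.56% | 2.80% | 0.18% |
| 2% | 3.9 | 9.45% | 3.91% | 0.44% |
| 3% | 5.9 | 8.49% | 4.46% | 1.09% |
| 5% | 9.8 | 6.56% | 4.33% | 2.05% |
| 10% | 19.6 | 5.23% | 5.17% | 2.83% |

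The likelihood-ratio maximum at these low rates is 9.46%, at p = 2.05%. The level exceeds 7% for p from 1.2% to about 4.4% and first passes 5% at about 0.95%. At 88 per arm the maximum is 9.43%, at p = 2.3%, so the arm size matters little.

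**Where the excess comes from.** Given the total number of events, the likelihood-ratio test cannot reject with 1 or 2 events. With 3 it rejects every 3–0 split, which has probability 24.6% under equal rates. With 7 it also rejects 6–1 splits (11.8% in all). Pearson does not reject in those two situations. This is why the level is low when events are almost absent, rises around 3 to 5 events, and then settles.

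**Source of the events.** SAP 8.1.3 and 8.2.4 refer to later procedures, and SAP 4.1 to the procedure page. Protocol 11.1 says that a further procedure to fragment or remove the stone is not an adverse event, so adverse event records need not contain it. The Protocol's schedule of events has no row for it. The documents therefore do not settle which record supplies STREAT.

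**The case against.** The strongest reply is that the premise of sparse data does not lead to the 9.5% figure. A reader might infer that, because the SAP expects almost no events, the true level is about 9.5%. The documents do not support that. With almost no events the test is conservative (1.64% at a 0.5% rate). The peak needs about 2% per arm, and no rate is given anywhere. The SAP 13 sentence is about the dropped analysis of counts. Its reason, exit at 30 days, carries over to the yes/no outcome, but it states no expected proportion. All of this stands.

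A reader might also infer that the trial's type I error is compromised. It is not. SAP 8.1.3 and 8.2.4 class this analysis as exploratory, it lies outside the sequence in SAP 5.5, and Protocol 6.6 does not require it for study success. Nor is the error tilted toward the device. The arms are equal and the test symmetric, so a false result in the device's favour has probability at most about 9.46%/2 = 4.7%. A 3 vs 0 split favouring the device has probability of at most about 2.8% under equal rates. Counts are shown beside the p-value, so a reader can see how few events there are.

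On the source of the events, one might conclude that STREAT will be built from basketing. That goes too far: SAP 4.1 also lists an other category, the CRF is not in the documents, and SAP 8.1.3 and 8.2.4 do say subsequent procedures. What remains is a conflict in wording.

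**Conclusion.** The point holds in a limited form. The planned test has no protection against small counts. Its exact level is 7% to 9.5% if the common re-intervention rate is about 1.2% to 4.4% per arm, below 5% for rates under about 0.9%, and near nominal by 10%. These figures assume 98 per arm and independent subjects with equal rates; 88 per arm gives almost the same peak. Which range applies cannot be told from the documents. The consequence is one exploratory p-value that could mislead in either direction. The conflict between SAP 4.1 and SAP 8.1.3 is a separate matter that needs no event-rate assumption and should be settled before programming.

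**What to change.** 1. Report the Pearson chi-square p-value in place of the likelihood-ratio one, with a 95% CI for the difference in proportions that copes with a zero cell. The planned PROC FREQ call with the chisq option already produces Pearson; the interval needs an additional request. At 98 per arm Pearson's level is 1.3% to 5.2% for rates of 1% to 10%. Fisher's exact test is acceptable but very conservative here (0.4% at a 2% rate), and its result is not in the output table the code now saves.
2. Record the change of test from Protocol 10.8 in SAP 13, which now says that there are no further changes.
3. Reconcile SAP 4.1 with SAP 8.1.3 and name the post-procedure records from which STREAT is derived, so that index-procedure basketing is not counted as re-intervention.
4. State the follow-up period the endpoint covers, and how events are handled in the subset followed to Day 90, who are observed longer than the rest.

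The cost is SAP wording and a few lines of code; no new visits or subjects are needed. The downside is fewer nominally significant results, including some loss of sensitivity to a real difference when events are few.
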